Interleukin-2 (IL-2) has been extensively studied in HIV infected individuals with no demonstrated clinical benefit as far as improving survival or decreasing risk of progression to AIDS. The results of the two landmark, international, multicenter, phase III, randomized trials of IL-2 in HIV infected participants (SILCAAT and ESPRIT) have been recently published. These trials, which started more than a decade ago, enrolled over 5800 participants who were randomized to anti-retroviral therapy (ART) +/- IL-2 and showed no benefit to IL-2 treatment in survival or progression to AIDS. Many individuals with HIV infection can lead normal lives on ART but replication-competent virus remains within resting CD4+ cells, referred to as the "HIV reservoir". There is a renewed interest in strategies to decrease or eliminate the viral reservoir in an attempt to provide a sterilizing or a functional "cure" for HIV that would allow the discontinuation of ART, which currently must be taken life-long. These therapies have long-term metabolic and cardiovascular toxicities as well as substantial cost. More recent data suggest that IL-2 administration may decrease the size of the HIV reservoir, getting ART-treated participants closer to levels of HIV persistence that may ultimately allow for sterilizing or functional cure.

Purpose

The purpose of this pilot study is to examine the effects of eight 4-day cycles of subcutaneous recombinant interleukin-2 (rIL-2) given every 8 weeks on levels of replication-competent HIV in CD4 cells and on the size of HIV viral reservoir in up to 20 participants with chronically suppressed HIV infection (viral load <50 copies/mL).

Design

Pilot open label trial of rIL-2 administration.

Power and Sample Size Considerations

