We base our sample size calculations on the primary analysis using a mixed effect model to estimate the effect of rIL-2 administration on the magnitude of the inducible reservoir by QVOA. In the Chun experiment (see below), the difference between the IL-2 and the HAART-only group was 0.64 IUPM, and the variance in the IL-2 group was 0.41. In a 200-simulation run, we estimate that a total sample size of 16 participants will provide an 80% power (95% CI, 0.74-0.84) to detect a difference from baseline to post-IL-2 administration as large as that seen in the Chun paper. Of note, these estimates are likely conservative, since the variation observed in repeated measurements with the optimized version of the QVOA assay that will be used in this study may be lower (variance around 0.11) than that of the assay used in the original Chun report (1).

1 Accelevir, data on file

Inclusion Criteria

Participants may enroll in the study if they meet the following criteria:

1. Written informed consent signed and dated by study participant.
2. Male or female, at least 18 years of age and not older than 65 years of age.
3. HIV-1 infection, documented by and FDA-approved ELISA, EIA, or rapid antibody detection method, and confirmed by a second approved antibody-based test or by a positive approved HIV RNA detection assay.
4. CD4+ T cell count ≥ 350 cells/mm 3 .
5. HIV-1 RNA < 50 copies/mL obtained within 60 days prior to study entry performed with an FDA-approved HIV-1 RNA assay.
6. Adequate venous access and no other contraindications for leukapheresis.
7. Absolute neutrophil count (ANC) ≥ 1500 /mm 3 .
8. Hemoglobin level >10 g/dL.
9. Platelet count $\geq 100,000$ /mm 3 .
10. Serum creatinine ≤ 1.5 mg/dL
11. AST and ALT <2.5 times the upper limit of normal
12. TSH, T3, and T4 levels within the normal range of the processing laboratory.
13. Anti-thyrosine peroxidase (TPO) within the normal range of the processing laboratory.
14. Willing to comply with study-mandated evaluations; including not changing antiretroviral regimen (unless medically indicated) during the study period.
15. All participants must have received HAART, and had viral loads below the limit of quantification of the assay for at least 1 year. Participants who had intermittent isolated episodes of detectable low-level viremia < 500 copies RNA/mL flanked by viral loads below the limit of quantification of the assay will remain eligible.

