11. Use of chronic corticosteroids, hydroxyurea, or immune-modulating agents (e.g., interleukin-2, interferon-alpha or gamma, granulocyte colony stimulating factors, etc.) within 30 days prior to enrollment.
NOTE: Use of inhaled or topical steroids is not exclusionary.
12. Breast-feeding.
13. Use of aspirin, warfarin or any other antithrombotic or antiplatelet agent during the 2-week period prior to leukapheresis.
14. History of autoimmune disorders, including but not limited to Crohn's disease, scleroderma, thyroiditis, inflammatory arthritis, myasthenia gravis, glomerulonephritis, systemic lupus erythematosus, and vasculitis.
15. Type 1 diabetes mellitus.
16. History of thyroid disease that has required antithyroid or thyroid hormone replacement therapy at any time in the past.
17. Current continued use, or anticipated continued medical indication for nephrotoxic agents, including but not limited to aminoglycosides and other potentially nephrotoxic antimicrobials, indomethacin, high scheduled doses of other NSAIDs, and lithium salts.
NOTE: Low doses or limited duration of these agents (i.e., ≤14 days) is not exclusionary.
18. Current continued use, or anticipated continued medical indication for hepatotoxic agents, including but not limited to amiodarone, methotrexate, and anticonvulsants and antimicrobials with elevated hepatotoxic potential.
NOTE: Low doses or limited duration of these agents (i.e., ≤14 days) is not exclusionary.
19. Active drug or alcohol use or dependence that, in the opinion of the investigator, would interfere with adherence to study requirements.
20. Serious illness requiring systemic treatment and/or hospitalization within 30 days prior to study entry that in the judgement of the investigator may compromise study participation or pose additional risks to the participant.
21. Any other condition that, in the opinion of the clinical investigator or sponsor, might compromise any aspect of this trial.

Study Treatment

All 20 participants will receive subcutaneous rIL-2 therapy in addition to combination antiretroviral therapy. Any combination of three FDA-approved antiretrovirals may be used.

Recombinant IL-2 at a dose of 5 MIU twice daily will be given subcutaneously for 4 consecutive days every 8 weeks for eight cycles.

Blood will be drawn for CD4 cell counts, for viral load, for routine safety monitoring and for HIV reservoir assays as detailed in section D.3.5 of the protocol.

Safety Monitoring

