The purpose of this pilot study is to observe the effects of up to eight 8-weekly cycles of subcutaneous recombinant interleukin-2 (SC rIL-2) on levels of replication-competent HIV in blood CD4 T cells in 20 participants with chronically suppressed HIV infection (viral load <50 copies/mL) who are stable on the same ART regimen for at least one year and have a CD4 T cell count ≥ 350 cells/mm³. We hypothesize that IL-2 administration will result in a reduction of the replication-competent reservoir, as measured by the QVOA assay, compared to the baseline values in this population.

B.1. STUDY ENDPOINTS AND OUTCOME MEASURES

The primary endpoint of the study is the change in the level of replication-competent virus from baseline to the end of rIL-2 treatment, as measured by the Quantitative Viral Outgrowth Assay (QVOA).

B.2. PRIMARY OBJECTIVE

The primary objective will be to compare levels of replication competent HIV in circulating CD4 T cells before and after up to 8 cycles of rIL-2 administration. The frequency of CD4 T cells containing replication-competent virus in leukapheresis samples obtained at baseline and at the end of rIL-2 treatment will be enumerated using several state of the art methods. The primary readout for this objective will be measurement of replication-competent virus by Quantitative Viral Outgrowth Assay (QVOA) performed by [name]'s group at Accelevir.

B.3. SECONDARY OBJECTIVES

- 1) To examine the relationships between levels of replication competent HIV as identified by QVOA and other measures of HIV persistence:
 - a) the intact proviral DNA assay ([name]),
 - b) the Envelope Detection by Induced Transcription-based Sequencing (EDITS, [name]) performed on the same pre-trial and post-trial leukapheresis samples.
- 2) To explore the effects of rIL-2 administration on induction of HIV expression in vivo as measured by the EDITS assay and plasma HIV levels.
- 3) To examine the effects of rIL-2 administration on natural killer cell phenotype and function and on the ability of NK cells to limit HIV propagation in vitro.

C. METHODS

C.1. STUDY DESIGN

This is an open label pilot study of 20 participants with chronically suppressed HIV infection (viral load <50 copies/mL), stable on an ART regimen for at least one year, who have a CD4 T cell count ≥ 350 cells/mm³. All participants will receive rIL-2.

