- c. Use each of the alternate readouts as the outcome to obtain estimates of the effect size on each of those assays, and then, fit a reverse regression model to estimate the effect of treatment on *any* of the readouts for which a treatment effect is demonstrated. While many approaches are available for this type of problem, reverse regression has the appealing feature for this small-size trial of not being as overly penalizing as more traditional approaches to the multiplicity problem, such as Bonferroni-like corrections (60). We will also use conventional nonparametric correlation analyses and the intraclass correlation coefficient derived from mixed effects models using each of the readouts to assess how the various readouts relate to one another.
- d. We will then fit models with time-updated total CD4 T cell count as a covariate. These models will allow us to establish how much of the variation in the change of the measured reservoir size is attributable to the expected CD4 T cell increase due to IL-2 administration. We do not believe that, if the magnitude of the effect is similar to the difference observed between the IL-2 alone and the HAART alone groups in the Chun paper, this can be explained simply by a dilutional effect, but this will be tested more formally in this phase of the analysis.

C.2.2. Power and Sample Size Considerations

We base our sample size calculations on the primary analysis using a mixed effect model to estimate the effect of IL-2 administration on the magnitude of the inducible reservoir by QVOA. In the Chun experiment, the difference between the IL-2 and the HAART-only group was 0.64 IUPM, and the variance in the IL-2 group was 0.41. In a 200-simulation run, we estimate that a total sample size of 20 participants will provide an 80% power (95% CI, 0.74-0.84) to detect a difference from baseline to post-IL-2 administration as large as that seen in the Chun paper. Of note, these estimates are likely conservative, since the variation observed in repeated measurements with the optimized version of the QVOA assay that will be used in this study may be lower (variance around 0.11) than that of the assay used in the original Chun report(2).

C.3. INCLUSION CRITERIA

Participants may enroll in the study if they meet the following criteria:

1. Written informed consent signed and dated by study participant.
2. Male or female, at least 18 years of age and not older than 65 years of age.

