Staff will contact the participant by phone to assess tolerance and compliance with injection schedule

D.2.10. End of Study Visit (or Premature Discontinuation Visit)

NOTE: The end of study visit should take place 8 weeks (+/- 2 weeks) after Day 0 of the last (8th) treatment cycle. In the case of premature discontinuation, the end of study visit should take place at least 6 weeks after day 0 of the last treatment cycle and may take place up to 10 weeks after day 0 of the last treatment cycle.

These visits will include:

- Interval history and targeted physical examination.
- Immunogenicity testing
- CD4+ and CD8+ T cell count (both absolute and as percent of lymphocytes)
- Plasma HIV RNA level by PCR (using the locally available assay)
- IL-2 immunogenicity
- At this visit the participant will undergo a 4 Liter leukapheresis at the Seidman Ambulatory Stem Cell Transplant Unit at University Hospitals using AIDS protocol 328.
- Plasma will be cryopreserved for single copy HIV RNA assay
- Leukapheresis product PBMC will be cryopreserved for:
 - HIV reservoir assay by EDITS
 - HIV reservoir assay by QVOA
 - Total and intact proviral DNA assay (Accelavir)
 - Assays of immune cell phenotype and NK cell phenotype

If leukapheresis cannot be done after premature treatment discontinuation for any reason, a 120 cc. blood draw will be obtained for preparation of PBMC and plasma. Based upon cell yield these samples will be used for:

- Plasma will be cryopreserved for single copy HIV RNA assay
- HIV reservoir assay by EDITS
- HIV reservoir assay by QVOA
- Total and intact proviral DNA assay (Accelavir)
- Assays of immune cell phenotype and NK cell phenotype

D.2.11. Immunogenicity follow-up

Participants who have detectable neutralizing antibodies at the end of study visit will be followed approximately every 90 days for repeat testing until 12 months after the end of study or until a negative result is obtained. During these visits, an interval medical history and targeted physical exam will be conducted. If clinically significant events have occurred, the participant will be referred for appropriate medical care.

D.2.12. Management of off-window visits

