The SMC will review accrual, toxicity summaries, off-treatment and off-study rates, and reasons broken down by study arms. Meetings of the SMC are described above. The SMC will be asked to consider the following regarding safety events: the grade of the event, the time to resolution (if any), and the site clinician's judgment of the relationship to treatment. The first interim safety review by the SMC is planned 3 months after the first subject enrolls and approximately every 3 months thereafter, but expedited reviews will occur whenever the threshold for temporary enrollment discontinuation is reached. Criteria for temporary enrollment discontinuation and expedited SMC review are:

- Three or more participants have experienced a grade 3 AE that is deemed possibly, probably, or definitely related to study treatment
- Two or more participants have experienced a grade 4 AE that is deemed possibly, probably, or definitely related to study treatment
- Any death occurs on study that is deemed possibly, probably, or definitely related to study treatment

The SMC will review the events whenever any of the criteria above is met, and recommend, based on the results of the review, whether the study can proceed as planned, proceed with modifications, or be discontinued.

I.4. Human Subjects Involvement, Characteristics, and Design

Up to 20 participants will be enrolled in the clinical trial. Potential participants will be recruited primarily from the Special Immunology Unit, the HIV clinic of University Hospitals Cleveland Medical Center, although recruitment from other area hospitals through direct outreach and targeted advertisement is also possible. Characteristics of the study population, inclusion/exclusion criteria, and planned study procedures are described in the clinical protocol. No vulnerable populations will be included in these studies.

I.5. Sources of Materials

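### The synopsis and section C.2.2 claim the same 80% power from the same printed inputs, for 16 and for 20 participants, and nothing reconciles them

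*Combined protocol and SAP*

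**What the plan says.** The power paragraph appears twice, in the synopsis (Power and Sample Size Considerations) and in section C.2.2. Both base the calculation on the mixed-model primary analysis of QVOA. Both take from the earlier IL-2 study a difference of 0.64 IUPM between groups and a variance of 0.41 in the IL-2 group, and both cite a 200-simulation run. They then part:

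- Synopsis: "we estimate that a total sample size of 16 participants will provide an 80% power (95% CI, 0.74-0.84")
- C.2.2: "we estimate that a total sample size of 20 participants will provide an 80% power (95% CI, 0.74-0.84")

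Both close by calling the estimate probably conservative, because repeat measurements with the newer assay may have a variance near 0.11.

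Elsewhere the trial size is 20 or a ceiling of 20. Section C.1 says "This is an open label pilot study of 20 participants with chronically suppressed HIV infection", and the synopsis under Study Treatment says "All 20 participants will receive subcutaneous rIL-2 therapy in addition to combination antiretroviral therapy". The synopsis under Purpose says "in up to 20 participants with chronically suppressed HIV infection", and section I.4 says "Up to 20 participants will be enrolled in the clinical trial". Sixteen appears as a sample size only in the synopsis power paragraph. The text supplied gives no attrition allowance and does not describe 16 as the evaluable number.

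**The concern.** Power rises with sample size, so a single set of inputs cannot give the same true power at 16 and at 20. Each paragraph calls its figure a total, so the text does not present one as evaluable and the other as enrolled.

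This paragraph is the trial's only quantitative design justification, and the number of complete pre/post QVOA pairs may well fall below 20. Enrolment is a ceiling. For early stoppers, section D.2.10 says "If leukapheresis cannot be done after premature treatment discontinuation for any reason, a 120 cc. blood draw will be obtained", and of that smaller sample "Based upon cell yield these samples will be used for" the listed assays, QVOA among them. A reader cannot tell whether 16 complete pairs would meet the design target.

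Two further weaknesses make the conflict hard to resolve from the documents:

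- Section A.2 describes the source study as cross-sectional, comparing different people. Its 0.64 and 0.41 do not supply the variance of within-person change, which is what section C.2.1 tests.
- The reassurance about conservatism sets a group variance (0.41) beside variation in repeat assay measurements (0.11). As described, these are different kinds of variance.

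**Working it through.** **Inputs.** From the synopsis and C.2.2: effect d = 0.64; post-treatment variance 0.41; N = 16 or 20; power 80%; 200 simulations. Not stated: alpha, sidedness, baseline variance Vb, pre/post correlation ρ. I assume alpha 0.05, two-sided, and also try one-sided.

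**Method.** With complete pairs and a test of within-person change, Vb and ρ act only through the variance of change, V = Vb + 0.41 − 2ρ√(0.41·Vb). I therefore solve for the V that gives 80% at one N and apply it at the other.

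**Can the printed 80% be reproduced?** Only by supplying the missing inputs. As an illustration, take Vb = 0.41 and ρ = 0, so V = 0.82 (two-sided 0.05):

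| Test | N = 16 | N = 20 |
|---|---|---|
| Paired t | 75.3% | 85.0% |
| Normal | 80.7% | 88.5% |
| Random-intercept REML, simulated, t to Wald z | 78.6-82.9% | 87.3-89.8% |

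The normal version matches 80% at 16. The paired t misses by about 5 points in each direction. This does not decide between the two numbers, because Vb and ρ are assumed.

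**Cross-power, normal test.** Power = Φ(d/√(V/N) − 1.960), so 80% needs d/√(V/N) = 1.960 + 0.842 = 2.802.

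- V for 80% at 16: 16 × 0.64² / 2.802² = 0.835.
- V for 80% at 20: 20 × 0.64² / 2.802² = 1.044. The ratio is 20/16 = 1.25.
- If 80% holds at 20, power at 16 = Φ(2.802 × √(16/20) − 1.960) = Φ(0.546) = 70.7%.
- If 80% holds at 16, power at 20 = Φ(2.802 × √(20/16) − 1.960) = Φ(1.172) = 87.9%.

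**Cross-power, both tests** (paired t by the noncentral t distribution):

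| Test | V for 80% at 16 | V for 80% at 20 | Power at 16 if 80% at 20 | Power at 20 if 80% at 16 |
|---|---|---|---|---|
| Two-sided, t | 0.729 | 0.939 | 69.5% | 88.8% |
| Two-sided, normal | 0.835 | 1.044 | 70.7% | 87.9% |
| One-sided, t | 0.964 | 1.231 | 71.1% | 87.8% |
| One-sided, normal | 1.060 | 1.325 | 71.9% | 87.2% |

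The two-sided variance of change must be 25% (normal) to 29% (t) larger for 20 than for 16. At ρ = 0, subtracting 0.41 gives a baseline variance of 0.32-0.43 for 16 and 0.53-0.63 for 20. No baseline variance is printed to test either range.

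**Incomplete pairs.** If 18 of 20 give both samples (my assumption; two-sided), power is 75.2% (t) or 75.7% (normal) when C.2.2 is right, and 85.0% or 84.4% when the synopsis is right.

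**Monte Carlo error.** The 95% half-width at 80% is 1.96 × √(0.8 × 0.2/200) = 0.055 with 200 replicates, and 0.018 with 2,000.

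**The case against.** The strongest reply has four parts.

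*The effect on the trial is small.* Enrolment is consistently 20 or up to 20, 16 appears once, and no analysis or stopping rule depends on it. With Vb = 0.41, non-negative correlation and complete pairs, power at 20 is at least 85%. This stands, and it is why the point makes no claim of inadequate power.

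*Only the printed inputs agree.* Two runs could have differed in correlation, covariates or attrition, and a simulation with dropout built in could properly attach 80% to a total of 20. That is possible, but neither section says so. If it is the explanation, printing it resolves the conflict.

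*Simulation noise could hide the gap.* With 200 replicates, true powers of about 74-75% at 16 and 84% at 20 (for example V = 0.845 by paired t, giving 74.0% and 84.0%) would both be compatible with the printed interval. This is correct. But noise cannot make the true powers equal, nothing says that two runs were made, and an estimate that cannot separate 16 from 20 is a reason for more replicates.

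*The 0.11 is cited to data on file, so its nature cannot be checked.* If it is a within-person variance on the same scale and response is homogeneous, V = 2 × 0.11 = 0.22 and paired-t power exceeds 99% at either number, so the reassurance could be right in direction. That is fair. What stands is that the sentence, as written, does not show 0.11 to be comparable with 0.41.

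**Conclusion.** The contradiction holds. The plan states the same power and interval for two sample sizes from the same printed inputs, without a stated link. As complete-data figures under one set of inputs they are about 8 to 10 percentage points apart (two-sided 0.05): roughly 70-71% at 16 if C.2.2 is right, or 88-89% at 20 if the synopsis is right. One-sided testing gives 71-72% and 87-88%.

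These figures rest on an assumed alpha of 0.05, complete pairs and a test of within-person change; they do not depend on the unstated baseline variance or correlation. A mixed model that also uses single-visit data would shift them somewhat.

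Which number is right cannot be settled from the documents. The practical consequence is modest if all 20 participants provide both samples, and larger if pairs are lost.

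**What to change.** In both the synopsis and C.2.2:

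1. State one evaluable sample size (participants with both QVOA results) and one enrolled number. Say whether the gap is an allowance for loss, and how large.
2. Re-run the simulation once with more replicates, for example 2,000. Report alpha, sidedness, the baseline and post-treatment variances (or the variance of change), a range of pre/post correlations, the measurement scale and the assumed attrition. Take the stated power from that run, not from the figures here.
3. Qualify the sentence calling the estimate conservative, or remove it unless 0.11 is shown to be a comparable variance on the same scale.

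The cost is one short simulation and wording in two sections. The stated power may come out less favourable. No extra participants, visits or samples are needed.

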Many novel strategies are being explored in an effort to completely eradicate HIV infection. The majority will likely fail and, for the reasons outlined above, even those that reliably decrease the size of the HIV reservoir may be insufficient to cure HIV. We still do not have a sense that there exists a level of reservoir reduction — without complete elimination — that would suffice to result in durable control of HIV as defined by the sustained absence of viremia after discontinuation of antiretroviral therapy. In this regard, the limits of our ability to monitor virus persistence make it impossible to know if every infectious virus has been eliminated from the one person who has been cured. In that patient, replacement of the entire immune cell pool with cells resistant to HIV likely rendered the emergence from latency of any residual infectious virus incapable of amplification. There is reason to suspect that administration of interleukin-2 may have significant impact on the size of the HIV reservoir.

A.2. INTERLEUKIN-2 AND THE HIV RESERVOIR

Exogenous administration of interleukin-2 has been explored as a strategy to purge HIV from latently infected CD4+ T cells and thus reduce the viral reservoir (13-15). The rationale for this approach was the observation that in a pooled analysis of three of the phase II randomized studies of rIL-2 (16) the mean decrease from baseline plasma HIV RNA was significantly greater in patients randomized to receive rIL-2 plus ART versus ART alone, and that *in vitro* IL-2 can be used to activate latent integrated virus (13). Chun et al reported a cross sectional analysis of reservoir size among 26 ART treated participants who had been treated with ART alone or ART plus an average of 10 cycles of interleukin-2 (IL-2). IL-2 had been administered with an eye to increasing circulating CD4+ T cells as was the

[figure not shown]

Fig. 1 Frequency of resting CD4⁺ T cells containing replication-competent HIV-1. Patients receiving IL-2 plus HAART (**a**) or HAART alone (**b**) were assessed by activation of purified resting CD4⁺ T cells on day 0 (with duplicates of 10 million cells per well) and determination of IUPM (vertical axis). Horizontal axis, patient identification number.

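### The power statement is unsupported as written: the variance of within-person change is never given, and the same 80% is printed for 16 and for 20 participants

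*Combined protocol and SAP*

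**What the plan says.** Section C.2.2 (Power and Sample Size Considerations) bases the sample size on a mixed effects analysis of QVOA. It takes two figures from the earlier IL-2 study: "the difference between the IL-2 and the HAART-only group was 0.64 IUPM", and "the variance in the IL-2 group was 0.41". Section A.2 describes that study as "a cross sectional analysis of reservoir size among 26 ART treated participants", 14 on ART plus IL-2 and 12 on ART alone. "In a 200-simulation run", Section C.2.2 finds 80% power ("95% CI, 0.74-0.84") with 20 participants to detect a change of that size from baseline to after treatment. It then says that "these estimates are likely conservative, since the variation observed in repeated measurements with the optimized version of the QVOA assay" may be lower, at about 0.11, than with the assay used in the earlier study; the source is laboratory data on file. The synopsis paragraph on power gives the same power and the same interval for 16 participants.

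Sections B and C.2.1 make this a single-arm comparison of each person with his or her own baseline. Alpha, sidedness, within-person correlation, variance of change and any allowance for dropout are not stated.

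**The concern.** Three different variances are in play.

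- The 0.41 is a spread across different people measured once. It mixes stable differences between people with assay error.
- The 0.11 is a repeat-measurement variance, so it describes assay error only.
- The test needs the variance of within-person change: assay error at two visits, plus biological fluctuation, plus differences between people in how much the reservoir truly changes.

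Neither printed figure is the third quantity. A small repeat-assay variance therefore does not show that the power calculation has a margin. No repeat-measurement variance for the earlier assay is given either, so the reader's only available comparator for 0.11 is 0.41, which is a different component.

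A null result from this trial will be read against the stated power. If that power could lie well above or well below 80%, and if it is attached to two sample sizes, the reader cannot tell what a null result rules out.

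**Working it through.** **Inputs.** Difference 0.64, variances 0.41 and 0.11, 200 simulations, and N = 20 (Section C.2.2) or N = 16 (synopsis). Assumed because the documents are silent: two-sided 5%, no dropout, no covariates, and a paired t test as a stand-in for the mixed model with two time points.

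**Formula.** Noncentrality = 0.64 × √N / √V, where V is the variance of within-person change. Power is the noncentral t probability beyond the critical value, 2.131 for N = 16 and 2.093 for N = 20.

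**Step 1: try to reproduce the printed 80%.** Suppose 0.41 applies at each time point with no correlation. Then V = 2 × 0.41 = 0.82.

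- N = 16: noncentrality 0.64 × 4 / 0.9055 = 2.83; power 0.75 (t) or 0.81 (normal approximation).
- N = 20: noncentrality 0.64 × 4.472 / 0.9055 = 3.16; power 0.85 (t) or 0.89 (normal approximation).

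The synopsis figure (16 participants, 80%) is reproduced by the normal approximation. The Section C.2.2 figure (20 participants, 80%) is not. It would need V of about 0.94 (t) or 1.04 (normal). With a correlation of 0.5, V = 0.41 and power is 0.96 at N = 16 and 0.99 at N = 20 (t). So 16 and 20 participants differ by about 8 to 10 points at V = 0.82, and the same 80% cannot describe both under one set of inputs.

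**Step 2: what the 0.11 implies.** Put V = 2 × 0.11 + T. T is the person-to-person variation in true change plus biological fluctuation. The documents give no value, so T is an assumption shown over a range.

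| T | V | Power, N = 16 | Power, N = 20 |
|---|---|---|---|
| 0 | 0.22 | >0.99 | >0.99 |
| 0.41 | 0.63 | 0.85 | 0.93 |
| 0.60 | 0.82 | 0.75 | 0.85 |
| 1.0 | 1.22 | 0.58 | 0.69 |

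At N = 20, power falls below 80% once V exceeds 0.94, that is once T exceeds 0.94 − 0.22 = 0.72. At N = 16 the limit is V = 0.73, or T = 0.51.

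**Step 3: the printed interval (minor).** For 160 of 200:

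- Wilson: 0.739 to 0.8495, printed as 0.74–0.85.
- Exact: 0.738 to 0.853, also 0.74–0.85.
- Wald: 0.745 to 0.855, printed as 0.74–0.86.

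The printed upper limit of 0.84 is 0.01 below the Wilson and exact values. Rounding the lower Wilson limit and truncating the upper one gives exactly 0.74–0.84.

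**The case against.** The best defence has three parts.

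*The sentence compares assay with assay.* It sets the new assay's variation against that of the earlier assay, not 0.11 against 0.41, and it is hedged. That is a fair reading. But the earlier assay's repeat variance is not given, so the comparison cannot be checked, and a better assay lowers only one part of the variance of change.

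*The direction may favour the plan.* Stable differences between people cancel in a before-after design. If the simulation used 0.41 at each visit with no correlation, true power is higher than simulated unless T exceeds about 0.60. This stands. A reader might infer that the label is false or that the trial is underpowered; the documents support neither, because T is unknown in both directions. In Section A.2, 8 of the 14 IL-2-treated people were at or below the detection limit, which may have compressed the 0.41. The same floor could also compress post-treatment values here, so the net effect on power is not established.

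*The interval is a rounding matter.* A reader might infer that it could not have come from 200 runs. That is too strong: mixed rounding and truncation explain it, and it has no effect on the design. Nor are 200 runs generally too few to separate 75% from 85% power. A result of 150/200 (Wilson 0.686–0.805) excludes 0.85, and 170/200 (0.794–0.893) excludes 0.75. Only an estimate near 0.80 is marginal against both, and the printed interval already shows that.

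On the 16 and the 20, an unstated 20% dropout allowance would link them (16 / 0.8 = 20). But Section C.2.2 attaches the 80% to 20 participants directly and mentions no dropout.

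**Conclusion.** The power statement needs correcting. The claimed margin is unsupported because the variance that drives the test is missing. Depending on T, power with 20 participants could be above 0.99 or as low as 0.69 over the range shown, and with 16 participants above 0.99 or as low as 0.58. These figures rest on the assumed two-sided 5%, the paired t approximation and full follow-up. The identical result for 16 and 20 participants is an internal contradiction that depends on no assumed value of T. The 0.01 slip in the interval is minor. No test or decision rule is shown to be wrong, and the sample size itself is not shown to be inadequate.

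**What to change.** In Section C.2.2 and the synopsis:

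- Delete the conservative label, or justify it with the variance of within-person change on the analysis scale.
- Reconcile 16 with 20, and state any dropout allowance if that is the explanation.
- State alpha, sidedness and the assumed within-person correlation or SD of change.
- Replace the single 80% with a short table of power at the actual N over a plausible range of that SD, covering both assay error and biological variation. Use a larger simulation run and print the interval that matches it.

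The cost is a short rerun and some rewording. The stated power may look less favourable than it does now.
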